### **6.5.1.2 Systemic events**

The systemic events assessed and recorded in the e-diary are vomiting, diarrhea, headache, fatigue, myalgia, arthralgia, chills, and fever from within seven days after each IMP dose administration. The derivations for systemic events will be handled in a similar way to how local reactions are handled for presence of event, severity level, duration, and onset day (latency time).

Fever is defined as an oral body temperature  $\geq 38.0^{\circ}\text{C}$  ( $100.4^{\circ}\text{F}$ ). Temperatures collected in degrees Fahrenheit will be converted to degrees Celsius using  $(^{\circ}\text{F} - 32) \times 5/9$  and grading will be based on the unrounded conversions.

The oral body temperature for each day will be recorded in the e-diary and temperature from Day 1 through Day 7 will be graded as described in [Table 6](#).

Solicited systemic events will be categorized as mild, moderate, severe or potentially life-threatening) and graded from 1 to 4, during the analysis as described in [Table 6](#).

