8.2.5.2 Assessments of intensity for systemic reactions

Symptoms of systemic reactions will be assessed as absent, mild, moderate, or severe according to the grading scale in [Table 5](#).

Table 5: Systemic reaction grading scale

	Mild (Grade 1)	Moderate (Grade 2)	Severe (Grade 3)	Potentially life-threatening (Grade 4) ^a
Vomiting	1 to 2 times in 24 h	>2 times in 24 h	Requires intravenous hydration	Emergency room visit or hospitalization for hypotensive shock
Diarrhea	2 to 3 loose stools in 24 h	4 to 5 loose stools in 24 h	6 or more loose stools in 24 h	Emergency room visit or hospitalization for severe diarrhea
Headache	Does not interfere with activity	Some interference with activity	Prevents daily routine activity	Emergency room visit or hospitalization for severe headache
Fatigue	Does not interfere with activity	Some interference with activity	Prevents daily routine activity	Emergency room visit or hospitalization for severe fatigue
Myalgia	Does not interfere with activity	Some interference with activity	Prevents daily routine activity	Emergency room visit or hospitalization for severe muscle pain
Arthralgia	Does not interfere with activity	Some interference with activity	Prevents daily routine activity	Emergency room visit or hospitalization for severe joint pain
Chills	Does not interfere with activity	Some interference with activity	Prevents daily routine activity	Emergency room visit or hospitalization for severe chills
Fever (oral temperature of $\geq 38.0^{\circ}\text{C}/\geq 100.4^{\circ}\text{F}$)	38.0°C/100.4°F to 38.4°C/101.1°F	38.5°C/101.2°F to 38.9°C/102.0°F	39.0°C/102.1°F to 40.0°C/104.0°F	>40.0°C/>104.0°F

a. Investigator or medically qualified person confirmation is required for all reactogenicity graded as Grade 4.

Source: Based on the US FDA guidance for industry ["Toxicity Grading Scale for Healthy Adult and Adolescent Volunteers Enrolled in Preventive Vaccine Clinical Trials"](#).

8.2.6 Subject e-diaries for assessment of reactogenicity (local and systemic reactions) – Trial site personnel and investigator tasks

Subject e-diaries will be issued, trained, and collected by trial site personnel at the visits given in the SoAs. Subject e-diaries will be issued, trained, and collected by trial site personnel at the visits given in the SoAs (Section 1.3 and Section 13.5).

The trial site personnel will ask/remind the trial subjects to:

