**Table 5: Local reaction grading scale**

	Mild (Grade 1)	Moderate (Grade 2)	Severe (Grade 3)	Potentially life-threatening (Grade 4)c
Pain	Does not interfere with activity	Interferes with activity	Prevents daily activity	Requires attendance at an emergency room or hospitalization for severe pain
Erythema / rednessa	2.5 cm to 5.0 cm (0.98 in to 1.96 in)	>5.1 cm to 10.0 cm (>1.96 in to 3.94 in)	>10 cm (>3.94 in)	Necrosis or exfoliative dermatitis
Induration / swellingb	2.5 cm to 5.0 cm	>5.1 cm to 10.0 cm	>10 cm	Necrosis

Source: Based on the US FDA guidance for industry [“Toxicity Grading Scale for Healthy Adult and Adolescent Volunteers Enrolled in Preventive Vaccine Clinical Trials”](#).

- a. In addition to grading the measured local reaction at the greatest single diameter, the measurement should be recorded as a continuous variable.
- b. Induration/swelling should be evaluated and graded using actual measurement.
- c. Investigator or medically qualified person confirmation is required for all reactogenicity graded as Grade 4.

For participants recording at least one local reaction within seven days after each trial IMP dose administration, in the case of different value between participant reported and investigator confirmed results, investigator confirmed result will be included in the analysis:

- The maximum severity grade is equal to the highest graded local reaction within the recording period.
- Duration will be calculated in days as the difference from the start of the first reported event to the resolution of the last reported event, inclusive. The resolution date for events lasting longer than 7 days will be recorded in the participant's adverse event case report form. If the resolution date is partial or missing, the duration will be considered unknown.
- Onset day, defined as the first day of reporting any severity, will be derived for each recorded local reaction. If a participant report changes in severity of the local reaction, only the first day of reporting that specific local reaction will be counted.

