**Table 6: Systemic events grading scale**

	Mild (Grade 1)	Moderate (Grade 2)	Severe (Grade 3)	Potentially life-threatening (Grade 4)a
Vomiting	1 to 2 times in 24 h	>2 times in 24 h	Requires intravenous hydration	Emergency room visit or hospitalization for hypotensive shock
Diarrhea	2 to 3 loose stools in 24 h	4 to 5 loose stools in 24 h	6 or more loose stools in 24 h	Emergency room visit or hospitalization for severe diarrhea
Headache	Does not interfere with activity	Some interference with activity	Prevents daily routine activity	Emergency room visit or hospitalization for severe headache
Fatigue	Does not interfere with activity	Some interference with activity	Prevents daily routine activity	Emergency room visit or hospitalization for severe fatigue
Myalgia	Does not interfere with activity	Some interference with activity	Prevents daily routine activity	Emergency room visit or hospitalization for severe muscle pain
Arthralgia	Does not interfere with activity	Some interference with activity	Prevents daily routine activity	Emergency room visit or hospitalization for severe joint pain
Chills	Does not interfere with activity	Some interference with activity	Prevents daily routine activity	Emergency room visit or hospitalization for severe chills
Fever (oral temperature of <math>\geq 38.0^{\circ}\text{C}/\geq 100.4^{\circ}\text{F}</math>)	$38.0^{\circ}\text{C}/100.4^{\circ}\text{F}$ to $38.4^{\circ}\text{C}/101.1^{\circ}\text{F}$	$38.5^{\circ}\text{C}/101.2^{\circ}\text{F}$ to $38.9^{\circ}\text{C}/102.0^{\circ}\text{F}$	$39.0^{\circ}\text{C}/102.1^{\circ}\text{F}$ to $40.0^{\circ}\text{C}/104.0^{\circ}\text{F}$	$>40.0^{\circ}\text{C}/>104.0^{\circ}\text{F}$

a Investigator or medically qualified person confirmation is required for all reactogenicity graded as Grade 4.

Source: Based on the US FDA guidance for industry "[Toxicity Grading Scale for Healthy Adult and Adolescent Volunteers Enrolled in Preventive Vaccine Clinical Trials](#)".

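### If temperature is collected in °F, the SAP's unrounded-°C rule leaves 101.2°F and 102.1°F without a fever grade, although Table 6 prints them as the start of Grades 2 and 3; the cm limits of Table 5 have a similar gap from 5.0 to 5.1 cm

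*SAP*

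**What the plan says.** **Fever.** SAP 6.5.1.2 states that diary "temperature from Day 1 through Day 7 will be graded as described in" Table 6. Both SAP 6.1.2 and SAP 6.5.1.2 convert °F to °C by (°F − 32) × 5/9, and "grading will be based on the unrounded conversions". The bands in SAP Table 6 are the same as those in Protocol Table 5 (Protocol 8.2.5.2):

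- Grade 1: "38.0°C/100.4°F to 38.4°C/101.1°F"
- Grade 2: "38.5°C/101.2°F to 38.9°C/102.0°F"
- Grade 3: "39.0°C/102.1°F to 40.0°C/104.0°F"
- Grade 4: above 40.0°C (104.0°F)

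**Size.** Redness and swelling are measured and then graded at analysis (Protocol 8.2.5.1, SAP 6.5.1.1). For redness, SAP Table 5 gives Grade 1 as "2.5 cm to 5.0 cm (0.98 in to 1.96 in" and Grade 2 as ">5.1 cm to 10.0 cm (>1.96 in to 3.94 in" (closing brackets left off). Swelling has the same cm limits and no inch limits.

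**Reporting.** The severity summary in SAP 6.5.1.1 lists an Any row and Grades 1 to 4, and SAP 6.5.1.2 uses the same layout for systemic events. Maximum severity is the highest graded reaction in the recording period. SAP 6.1.1 has a general rule that categorical summaries show a missing category when a value is missing.

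**The concern.** The unrounded-conversion rule makes °C the governing scale, but the °C bands of Table 6 are closed at one decimal and leave open intervals between grades. Two of the printed °F limits also do not convert to the °C limits beside them. The rule and the table therefore cannot both be followed for certain °F readings. Table 5 has a comparable break in its cm limits.

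These tables are the derivation rule for the severity part of the primary safety summaries, not background. A participant whose peak reading falls in a gap counts in the Any row and in no Grade 1 to 4 row. If another day's reading has a grade, the participant may instead be reported at that lower grade, because the maximum is taken over graded reactions. A programmer would have to invent a closure, and the reasonable closures differ by one grade. For 102.1°F, that difference decides whether the participant enters the Grade 3 or higher row of the safety overview (SAP 6.5.1.3).

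**Working it through.** **1. Check the printed °C/°F pairs.** °C = (°F − 32) × 5/9, and back by °F = °C × 9/5 + 32.

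| Printed pair | °F converted to °C | °C converted to °F | Agree to one decimal? |
|---|---|---|---|
| 38.0 / 100.4 | 38.000 | 100.40 | yes |
| 38.4 / 101.1 | 38.389 | 101.12 | yes |
| 38.5 / 101.2 | 38.444 | 101.30 | no |
| 38.9 / 102.0 | 38.889 | 102.02 | yes |
| 39.0 / 102.1 | 38.944 | 102.20 | no |
| 40.0 / 104.0 | 40.000 | 104.00 | yes |

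Four of the six pairs reproduce. The lower limits of Grades 2 and 3 do not, in either direction.

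**2. Locate the gaps.** In °F, 38.4 to 38.5°C is 101.12 to 101.30, and 38.9 to 39.0°C is 102.02 to 102.20. The only 0.1°F readings strictly inside are 101.2, since 69.2 × 5/9 = 38.444, and 102.1, since 70.1 × 5/9 = 38.944. From 100.4 to 104.0°F there are (104.0 − 100.4)/0.1 + 1 = 37 readings, so 2 of 37 are ungraded. No °C reading to 0.1° lies in a gap.

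**3. Compare the ways of closing the gap.**

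| °F reading | Unrounded °C, bands as printed | Printed °F limits | °C rounded to one decimal | °C bands made contiguous, each ending where the next begins |
|---|---|---|---|---|
| 101.1 | 1 | 1 | 1 | 1 |
| 101.2 | none | 2 | 1 | 1 |
| 101.3 | 2 | 2 | 2 | 2 |
| 102.0 | 2 | 2 | 2 | 2 |
| 102.1 | none | 3 | 2 | 2 |
| 102.2 | 3 | 3 | 3 | 3 |

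**4. Size limits, with 1 in = 2.54 cm.**

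- By the cm limits, 5.0 cm is Grade 1, 5.2 cm is Grade 2, and 5.05 and 5.1 cm are neither. On a 0.1 cm grid the only ungraded value is 5.1 cm.
- For redness, the inch limits meet at 1.96 in, which is 1.96 × 2.54 = 4.978 cm. A redness of 5.1 cm is 5.1/2.54 = 2.008 in, so Grade 2 by inches.
- A redness of 5.0 cm is 5.0/2.54 = 1.969 in, so Grade 1 by cm and Grade 2 by inches.

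**5. What one participant is worth.** Group sizes come from SAP Table 1 and SAP 6.1: 45 per active arm, and 90 for the pooled 3a/3b or 4a/4b groups. With Clopper-Pearson 95% limits (the upper limit for 0/n is 1 − 0.025^(1/n)), counting one participant as Grade 3 fever or not changes:

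- n = 45: from 0/45 (0%, 0 to 7.9%) to 1/45 (2.2%, 0.1 to 11.8%)
- n = 90: from 0/90 (0%, 0 to 4.0%) to 1/90 (1.1%, 0.03 to 6.0%)

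**The case against.** Several limits on this point are fair, and each rules out a stronger reading that someone might infer.

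- **That fever readings go ungraded whatever the unit.** The documents do not state the e-diary unit. If it is °C to 0.1°, no fever reading is affected. The one-decimal precision in Protocol 8.2.2 is in the vital-signs section and may not govern the diary. The SAP does state a Fahrenheit rule twice, so °F data are at least foreseen.
- **That redness of 5.1 cm has no grade at all.** It has no grade by cm but is Grade 2 by the printed inch limits. For redness the defect is a conflict between units; only swelling has an unqualified gap.
- **That an ungraded event disappears from the tables.** It still counts in the Any row. The list of severity rows in SAP 6.5.1.1 does not say that nothing else may appear, and the missing-category rule in SAP 6.1.1 could place it there. That would make the gap visible, but a measured temperature would be shown as a missing grade.
- **That trial conduct is affected.** The fever definition (38.0°C) and the Grade 4 fever limit (40.0°C) convert exactly. The pausing rules in Protocol 7.1.1 turn on fever above 40.0°C, on Grade 4 events, and on unsolicited events of Grade 3 or above, not on the boundaries in question.

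It can also be said that safety is descriptive, that few participants will have a maximum at exactly one of these values, and that a sensible programmer would close the gap. The first two stand. The third does not: the closures in step 3 disagree, and the choice belongs in the plan. Rounding to one decimal contradicts the SAP's own words and puts both readings one grade below their printed °F limits.

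**Conclusion.** The point holds as a small, exact inconsistency in the grading rule for the primary safety severity tables. For fever it is conditional on collection in °F to 0.1°. For swelling it holds on the cm limits as printed, at one value if size is recorded to 0.1 cm (the documents do not give that precision). For redness it is a disagreement between the cm and inch limits.

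Probably few participants are affected, since the seven-day maximum must fall on one of these values. The consequence is confined to the severity split of fever, redness and swelling; of the two temperatures, only 102.1°F bears on Grade 3 or higher. Nothing in the documents shows which limit was intended, and this review takes no view on that. The correction is worth making because it is cheap and removes an arbitrary programming choice.

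**What to change.** In the SAP:

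1. Reconcile the unrounded-conversion rule with the °C and °F limits of Table 6, so that every reading of 38.0°C or more receives exactly one grade. Correct any printed °F limit that does not match the °C limit chosen.
2. Make the Table 5 cm bands for redness and swelling contiguous.
3. Either state that size is graded in cm only, or make the redness inch limits match the cm limits.
4. Record the change in SAP Appendix 8.1, which at present reports no changes to the protocol-planned analyses.

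The sponsor chooses the limits. Protocol Tables 4 and 5 carry the same cm and temperature bands and should be aligned at the next amendment; none is needed for this alone.

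The cost is a small SAP revision, plus a rerun of the severity tables if they are already programmed. That is possible, since this is SAP version 4.0 and outputs for the Internal Review Committee are produced during the trial. No new data and no change to trial conduct are required.

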**Table 6: Systemic events grading scale**

	Mild (Grade 1)	Moderate (Grade 2)	Severe (Grade 3)	Potentially life-threatening (Grade 4)a
Vomiting	1 to 2 times in 24 h	>2 times in 24 h	Requires intravenous hydration	Emergency room visit or hospitalization for hypotensive shock
Diarrhea	2 to 3 loose stools in 24 h	4 to 5 loose stools in 24 h	6 or more loose stools in 24 h	Emergency room visit or hospitalization for severe diarrhea
Headache	Does not interfere with activity	Some interference with activity	Prevents daily routine activity	Emergency room visit or hospitalization for severe headache
Fatigue	Does not interfere with activity	Some interference with activity	Prevents daily routine activity	Emergency room visit or hospitalization for severe fatigue
Myalgia	Does not interfere with activity	Some interference with activity	Prevents daily routine activity	Emergency room visit or hospitalization for severe muscle pain
Arthralgia	Does not interfere with activity	Some interference with activity	Prevents daily routine activity	Emergency room visit or hospitalization for severe joint pain
Chills	Does not interfere with activity	Some interference with activity	Prevents daily routine activity	Emergency room visit or hospitalization for severe chills
Fever (oral temperature of <math>\geq 38.0^{\circ}\text{C}/\geq 100.4^{\circ}\text{F}</math>)	$38.0^{\circ}\text{C}/100.4^{\circ}\text{F}$ to $38.4^{\circ}\text{C}/101.1^{\circ}\text{F}$	$38.5^{\circ}\text{C}/101.2^{\circ}\text{F}$ to $38.9^{\circ}\text{C}/102.0^{\circ}\text{F}$	$39.0^{\circ}\text{C}/102.1^{\circ}\text{F}$ to $40.0^{\circ}\text{C}/104.0^{\circ}\text{F}$	$>40.0^{\circ}\text{C}/>104.0^{\circ}\text{F}$

a Investigator or medically qualified person confirmation is required for all reactogenicity graded as Grade 4.

Source: Based on the US FDA guidance for industry "[Toxicity Grading Scale for Healthy Adult and Adolescent Volunteers Enrolled in Preventive Vaccine Clinical Trials](#)".

Systemic events reported up to seven days post-Dose 1 and post-Dose 2 will be summarized in the same manner as local reactions (see Section [6.5.1.1](#) using the Safety Set and Dose 2 Safety Set. Participants without any reactogenicity data up to 7 days after each IMP dose administration will be excluded from the systemic events analysis. In addition, a listing of participants in the Safety Set with reported systemic events will be provided.

If data regarding local /systemic reactogenicity events were not entered into the e-diary tool as planned, and instead were recorded on the AE CRF page, SDTM data reconstruction will be implemented to align with the FDA guidance outlined in "[Submitting Study Datasets for Vaccines to the Office of Vaccines Research and Review](#)".

### 6.5.1.3 Adverse events

Non-serious AEs will only be collected as of first IMP dose administered while SAEs need to be recorded upon awareness starting once informed consent is given. For Cohorts 1 to 4, AE collection will start from Visit 0 and continue until Visit 4 (i.e., until 1 month follow-up post-Dose 1), and (for participants who consent to a second dose of IMP after issue of

protocol version 5.0) restart from Visit 7 and continue until Visit 9 (i.e., until 1 month follow-up post-Dose 2). For Cohort 5, AE collection will start from Visit 0 and continue until Visit 9 (1 month post-Dose 2). AESIs, SAEs, AEs that lead to trial participant discontinuation or withdrawal, and all AEs linked to confirmed COVID-19 cases will be recorded up to the last planned visit for participants who consent to a second dose of IMP. For participants in Cohorts 1 to 4 completing Dose 1 only, recording will continue until Visit 6 (6 months post-Dose 1). For participants in Cohort 5 completing Dose 1 only, recording will continue until the last scheduled visit (5 months post-Dose 1).

Summary tables will include AEs reported from each IMP administration up to 28 days after each IMP administration, SAEs and AESIs occurring from IMP Dose 1 up to 6 months after each IMP administration for participants in Cohorts 1 to 4 and SAEs occurring from IMP Dose 1 up to 3 months after last IMP administration for participants in Cohort 5. AEs leading to IMP discontinuation or trial withdrawal will be listed, and summarized when at least 10 events in all participants have been reported.

AEs/SAEs post-Dose 1 will be summarized by treatment group post-Dose 1 based on the Safety Set. AEs/SAEs post-Dose 2 will be summarized by treatment group post-Dose 2 based on Dose 2 Safety Set.

All AEs will be coded using the most recent version of the MedDRA® coding system and graded for severity using FDA guidance for “[Toxicity Grading Scale for Healthy Adult and Adolescent Volunteers Enrolled in Preventive Vaccine Clinical Trials](#)”. No imputation for missing grades will be performed.

If an AE is reported more than once for the same participant for a SOC / PT the AE will be counted once for this SOC / PT for the specified reporting period.

All AE (from post-dose) summary tables will be sorted alphabetically by SOC and PT within SOC, unless specified otherwise.

The Safety Set will be used for the summary of data reported during assessment period post-Dose 1 and prior to Dose 2 and Dose 2 Safety Set will be used for summary of data reported post-Dose 2.

## **Safety overview**

The number and percentage of participants reporting at least one of the below events within the time frame specified above will be summarized by treatment group for the participants.

- Solicited local reactions and systemic events
  - Local reactions
    - Grade  $\geq 3$
  - Systemic events
    - Grade  $\geq 3$

- AE
- Related AE
- AE with Grade  $\geq 3$
- Related AE with Grade  $\geq 3$
- AE leading to treatment discontinuation
- AE leading to trial withdrawal
- SAE
- Related SAE
- AESI
- Related AESI
- AESI with Grade  $\geq 3$
- Death

The following safety data will be summarized by PT nested within SOC. The number and percentage of participants meeting the endpoint will be presented by treatment group:

- AEs from each IMP dose up to 28 days after each IMP dose
- Related AEs from each IMP dose up to 28 days after each IMP dose
- Related AEs with Grade  $\geq 3$  from each IMP dose up to 28 days after each IMP dose
- SAEs from each IMP dose through 6 months after each IMP dose for Cohorts 1 – 4. For Cohort 5, SAEs from IMP Dose 1 through 2 months after IMP Dose 1, from IMP Dose 2 through 3 months after IMP Dose 2 and from IMP Dose 1 through 3 months after last IMP dose.
- Non-serious AEs with percentage greater than 5% from each IMP dose up to 28 days post each IMP dose (data from two intervals combined)

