9.2 Sample size determination

The sample size for each cohort is mainly driven by typical small dose escalation designs for early detection of potential safety and reactogenicity events. The sample size is not based on any formal hypothesis test.

For safety outcomes, Table 6 shows the probability of observing at least 1 AE for a given true event rate of a particular AE. For example, if the true AE rate is 2%, with approximately 90 subjects in a vaccine group, there is 84% probability of observing at least 1 AE. Cohort 5 has a lower N, however, the dose given to Cohort 5 will have already been tested within Cohort 4.

Table 6: Probability of observing at least 1 AE, by assumed true event rate

Assumed true event rate of an AE	N=20 (Cohort 5)	N=45 (Cohorts 1,2)	N=90 (Cohorts 3,4)
1%	0.18	0.36	0.60

Assumed true event rate of an AE	N=20 (Cohort 5)	N=45 (Cohorts 1,2)	N=90 (Cohorts 3,4)
2%	0.33	0.60	0.84
3%	0.46	0.75	0.94
4%	0.56	0.84	0.97
5%	0.64	0.90	0.99

Abbreviations: AE = adverse event; N = number of subjects.

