### Cohort 5:

OBJECTIVES	ESTIMAND *	ENDPOINTS
Primary objectives		
To describe the safety and tolerability of two doses of 30 µg BNT162b4 alone in healthy adults aged 18 to 55 years, with and without evidence of prior SARS-CoV-2 infection, who received at least three prior doses of an authorized RNA-based COVID-19 vaccine.	
The frequency of dosed participants with:
 
 
Solicited local reactions at the injection site recorded up to 7 d after each IMP dose.
 
Solicited systemic events recorded up to 7 d after each IMP dose.
 
Participants with at least one AE occurring up to 28 d after each IMP dose.
 
Participants with at least one SAE occurring up to 3 months after last dose.
 
 
The frequency of dosed participants with:
 
 
Abnormal hematology or chemistry laboratory values 7 d after each IMP dose.
 
Grading shifts in hematology or chemistry laboratory assessments between baseline and 7 d after each IMP dose.
 
 
The frequency of dosed participants with:
 
 
New ECG abnormalities 7 d after each IMP dose.
 
	
 
Solicited local reactions (pain, erythema / redness, induration / swelling)
 
Solicited systemic events (vomiting, diarrhea, headache, fatigue, myalgia, arthralgia, chills and fever)
 
AEs
 
SAEs
 
 
 
Hematology and chemistry laboratory parameters (see Section 10.3 of the CTP)
 
 
 
ECG abnormalities consistent with probable or possible myocarditis or
 

OBJECTIVES	ESTIMAND *	ENDPOINTS
		pericarditis as defined in the protocol
Exploratory objectives		
CCI		

Abbreviations: AE = adverse event; CCI

CCI COVID-19 = coronavirus disease 2019; d = day; ECG = electrocardiogram; CCI

CCI

IMP = investigational

medicinal product; CCI

SAE = serious adverse event; SARS-CoV-2 = severe

acute respiratory syndrome coronavirus 2; CCI

[figure not shown]
\* All assessments as described in the estimands will be conducted within the schedule of visits window.

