## 6 STATISTICAL ANALYSES

### 6.1 General considerations

In general, all the data summaries will be performed by the following treatment groups:

Age Strata	Cohorts	Treatment Group Description
$\geq 18$ years	3a, 3b	Dose 1: BNT162b2 (WT/OMI BA.4/5) 30 $\mu$ g + BNT162b4 15 $\mu$ g, Dose 2: BNT162b2 (OMI XBB.1.5) 30 $\mu$ g + BNT162b4 15 $\mu$ g ( $\geq 18$ y)
	4a, 4b	Dose 1: BNT162b2 (WT/OMI BA.4/5) 30 $\mu$ g + BNT162b4 30 $\mu$ g, Dose 2: BNT162b2 (OMI XBB.1.5) 30 $\mu$ g + BNT162b4 30 $\mu$ g ( $\geq 18$ y)
	1, 2, 3a, 3b, 4a, 4b	BNT162b2 (WT/OMI BA.4/5) one dose only ( $\geq 18$ y)
18-55 years	1	Dose 1 and Dose 2: BNT162b2 (WT/OMI BA.4/5) 30 $\mu$ g + BNT162b4 5 $\mu$ g (18-55y)
	2	Dose 1 and Dose 2: BNT162b2 (WT/OMI BA.4/5) 30 $\mu$ g + BNT162b4 10 $\mu$ g (18-55y)
	3a	Dose 1: BNT162b2 (WT/OMI BA.4/5) 30 $\mu$ g + BNT162b4 15 $\mu$ g, Dose 2: BNT162b2 (OMI XBB.1.5) 30 $\mu$ g + BNT162b4 15 $\mu$ g (18-55y)
	4a	Dose 1: BNT162b2 (WT/OMI BA.4/5) 30 $\mu$ g + BNT162b4 30 $\mu$ g, Dose 2: BNT162b2 (OMI XBB.1.5) 30 $\mu$ g + BNT162b4 30 $\mu$ g (18-55y)
	1, 2, 3a, 4a	BNT162b2 (WT/OMI +BA.4/5) 30 $\mu$ g one dose only (18-55y)
	5	Dose 1 and Dose 2: BNT162b4 30 $\mu$ g (18-55y)
>55 years	3b	Dose 1: BNT162b2 (WT/OMI BA.4/5) 30 $\mu$ g + BNT162b4 15 $\mu$ g, Dose 2: BNT162b2 (OMI XBB.1.5) 30 $\mu$ g + BNT162b4 15 $\mu$ g ( $>55$ y)
	4b	Dose 1: BNT162b2 (WT/OMI BA.4/5) 30 $\mu$ g + BNT162b4 30 $\mu$ g, Dose 2: BNT162b2 (OMI XBB.1.5) 30 $\mu$ g + BNT162b4 30 $\mu$ g ( $>55$ y)
	3b, 4b	BNT162b2 (WT/OMI BA.4/5) 30 $\mu$ g one dose only ( $>55$ y)
	1, 2, 3a, 3b, 4a, 4b, 5	All participants

“All participants” will be presented in disposition, baseline, and selected safety summary tables as specified.

No formal statistical comparisons between vaccine dose levels will be performed. Missing data, other than that described for AEs/Concomitant Medications/Vaccinations below will not be imputed.

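### The per-dose SAE percentages for Cohort 5 cover 2 and 3 months, against 6 months after each dose in Cohorts 1 to 4, and no matched-window row or person-time rate is planned.

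*SAP*

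**What the plan says.** SAP 6.5.1.3 (Safety overview) tabulates by system organ class and preferred term "SAEs from each IMP dose through 6 months after each IMP dose for Cohorts" 1 to 4. The same bullet gives Cohort 5 three windows: "For Cohort 5, SAEs from IMP Dose 1 through 2 months after IMP Dose 1", then "from IMP Dose 2 through 3 months after IMP Dose 2 and from IMP Dose 1 through 3 months after last IMP dose". The third is the window of the Cohort 5 primary estimand in SAP 1.1: "Participants with at least one SAE occurring up to 3 months after last dose". The introductory text of 6.5.1.3 sets the matching time frame for the other cohorts as "SAEs and AESIs occurring from IMP Dose 1 up to 6 months after each IMP administration for participants in Cohorts 1 to 4".

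The statistic is the number and percentage of participants by treatment group. Under SAP 6.1.1 the denominator for event data is N in the analysis set. SAP 6.1 states "In general, all the data summaries will be performed by the following treatment groups", and that list puts Cohort 4a (30 µg with the spike vaccine), the 18-55 controls and Cohort 5 (30 µg alone) in one age stratum. The visible text plans no common-window SAE row and no exposure-adjusted rate.

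**The concern.** SAEs are a primary endpoint, and with no hypothesis tested the displayed percentages are the result. Readers will set Cohort 5 beside Cohort 4a. Protocol 4.2 says Cohort 5 is meant to shed light on interaction between the components, and Protocol 9.2 defends its small size because "the dose given to Cohort 5 will have already been tested within Cohort 4". In the per-dose tables, shorter observation alone pulls the Cohort 5 percentage down. BNT162b4 alone could then look safer than the combination for a reason unrelated to the vaccine.

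**Working it through.** **The plan's own figures.** SAP Table 3 follows 1 − (1 − p)^n. At p = 0.02, n = 90 gives 0.838 (stated 0.84) and n = 20 gives 0.332 (stated 0.33). All 15 cells reproduce within 0.01. The documents give no SAE rate and no ratio between cohorts.

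**Inputs.**
- Windows, from SAP 6.5.1.3: 2 and 3 months against 6.
- Dose 2 timing, from SAP Table 1: 2 months in Cohort 5, 6 to 7 months in Cohorts 1 to 4.
- N, from SAP Table 1: 20 in Cohort 5, and 6 + 39 = 45 on the combination in Cohort 4a.
- SAE risk: assumed, 0.5% to 20% of participants per year.

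**Per-dose tables, equal and constant hazard.** With annual risk a, h = −ln(1 − a)/12 per month, and the expected percentage over t months is 1 − exp(−ht).

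| Assumed annual risk | 2 months | 3 months | 6 months | Ratio, Dose 1 (2 vs 6) | Ratio, Dose 2 (3 vs 6) | P(no SAE in Cohort 5 after Dose 1) |
|---|---|---|---|---|---|---|
| 0.5% | 0.08% | 0.13% | 0.25% | 0.334 | 0.500 | 0.98 |
| 2% | 0.34% | 0.50% | 1.01% | 0.334 | 0.501 | 0.93 |
| 5% | 0.85% | 1.27% | 2.53% | 0.336 | 0.503 | 0.84 |
| 20% | 3.65% | 5.43% | 10.56% | 0.346 | 0.514 | 0.48 |

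The ratios barely depend on the assumed risk.

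**Per-dose tables, hazard falling after each dose.** With half-life L, the cumulated hazard is proportional to 1 − 2^(−t/L).
- L = 1 month: Dose 1, 0.750/0.984 = 0.76; Dose 2, 0.875/0.984 = 0.89.
- L = 3 months: Dose 1, 0.370/0.750 = 0.49; Dose 2, 0.500/0.750 = 0.67.

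At the same hazard, a shorter window cannot count more participants, so the direction holds whatever the shape.

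**Cumulative window.** Cohort 5 covers about 2 + 3 = 5 months. Cohorts 1 to 4 cover 6 months after one dose and about 12 to 13 months after two. For rare events at a constant hazard, with Dose 2 uptake u in Cohort 4, the ratio is about 5/(6 + 6u):
- u = 0: 0.83
- u = 0.5: 0.56
- u = 2/3: 0.50
- u = 1: 0.42 (5/13, about 0.39, if 13 months are counted)

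This range needs the constant hazard. If risk is tied to dosing, a two-dose Cohort 5 participant has two risk periods where a one-dose Cohort 4 participant has one, so no direction is claimed for that row.

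**After the change.** Matched 2- and 3-month windows give an expected ratio of 1.00 for any common hazard. Person-time gives 1.00 when the hazard is constant: at 2% per year, 2.02 per 100 person-years in both cohorts.

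**The case against.** The strongest objection is that sample size, not window length, limits what Cohort 5 can show. With 20 participants the smallest non-zero percentage is 5%. At an assumed 2% per 6 months, the chance of no SAE after Dose 1 is 0.98^(20/3) = 87%; a full 6-month window would still leave it at 0.98^20 = 67%. The exact 95% upper limit for 0 of 20 is 1 − 0.025^(1/20), about 17%. This stands, and it is why the point is minor.

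Other parts also stand. The Cohort 5 windows are disclosed and follow its schedule: Dose 2 falls at 2 months and follow-up ends 3 months later. Cohort 5 is open-label and non-randomised, with a BMI limit of 30 rather than 35 kg/m², so matched windows would not make it fully comparable with Cohort 4a. The general AE tables already use 28 days after each dose in every cohort, and all SAEs are listed. Adjacent columns are inferred from SAP 6.1; the table shells are not in these documents. Protocol 9.2 justifies the cohort size and does not itself plan an SAE comparison. Protocol 4.2 mentions interaction alongside the T-cell response, without naming safety.

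None of this corrects the tabulated SAE percentages. A listing lets a careful reader re-cut the events, but the table still shows unequal windows.

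A reader might also infer that an all-participants column mixes the windows. The documents do not support that: SAP 6.1 limits the column to tables where it is specified, and 6.5.1.3 specifies it for no SAE table. The pooled groups aged 18 and over exclude Cohort 5.

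**Conclusion.** The point holds for the per-dose SAE tables. With equal and constant hazard, the expected percentage of Cohort 5 participants with an SAE is about one third of Cohort 4a's after Dose 1 and one half after Dose 2. These are lower bounds if the common hazard does not rise over time, since clustering after dosing moves the ratios towards 1. The cumulative primary-estimand row is also unmatched, at 0.39 to 0.83 under a constant hazard.

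A reader might infer that Cohort 5's SAE rate would be one third to one half of Cohort 4a's. That goes too far: at equal constant hazard the rate per person-time is the same, and only the percentage over the window shrinks. Nor does one third to one half describe the primary Cohort 5 row, where the ratio exceeds one half if Dose 2 uptake is below about 67%.

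This is a minor distortion in the expected value of a descriptive, non-randomised display. The estimands and follow-up are not in question.

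**What to change.** In SAP 6.5.1.3:

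1. Add SAE rows cut at 2 months after Dose 1 for Cohort 4a and the 18-55 controls, and at 3 months after Dose 2 for Cohort 4a. Define the cuts in days with the SAP's own conversion of 30.4375 days per month (2 months = 60.9 days, 3 months = 91.3 days). Use these rows when Cohort 5 is read beside those groups.
2. For the cumulative window, add SAEs per person-time, with the person-months shown. Note that this equalises the groups only if the hazard is roughly constant.
3. State the SAE window in each column heading or footnote.

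Keep the 6-month rows for Cohorts 1 to 4 and the Cohort 5 primary-estimand row as they are. Onset dates are already recorded (Protocol 10.4.3), so no new data are needed. The cost is SAP wording, some programming and a slightly longer SAE table.
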